
relapsed/refractory multiple myeloma.⁸³ These promising results corroborate with preclinical studies underscoring the scientific rationale for the drug development. Other clinical trials evaluating the efficacy of panobinostat in multiple myeloma are in active development.

Table 2-4. Summary of selected clinical trials of panobinostat in multiple myeloma

Agent(s)/Study	Phase	N	Panobinostat Dose	Clinical Efficacy	Safety
Panobinostat single agent (Wolf et al.) ⁷⁴	2	38	20 mg PO TIW weekly every 21 days	PR n=1; MR n=1; SD n=9	Grade 3/4 neutropenia 31.6%; grade 3/4 thrombocytopenia 26.3%; grade 3/4 GI 10.5%
Panobinostat + bortezomib + dexamethasone (San-Miguel et al.) ⁷⁸	1b	62	20 mg PO TIW every weekly every 21 days	CBR* 61.3%; ORR 51.6%; PR 35.5%; VGPR 9.7%; MR 9.7%	Grade 3/4 thrombocytopenia 80.6%; grade 3/4 neutropenia 59.7%; grade 3/4 asthenia 25.8%; grade 3/4 anemia 17.7%
PANORAMA 2 (panobinostat + bortezomib + dexamethasone: Richardson et al.) ⁷⁹	2	55	20 mg PO TIW on a 2-weeks-on/1-week-off schedule, every 21 days	CBR 52.7%; ORR 34.5%; SD 36.4%; PR 32.7%; MR 18.2%	Grade 3/4 thrombocytopenia 63.6%; grade 3/4 diarrhea 20%; grade 3/4 neutropenia 14.6%
PANORAMA 1 (panobinostat + bortezomib + dexamethasone vs. placebo: Richardson et al.) ⁸³	3	768	20 mg PO TIW on a 2-weeks-on/1-week-off schedule, every 21 days	Median PFS 12 months vs. 8.1 months; ORR 61% vs. 55%; nCR/CR 28% vs. 16%	Grade 3/4 thrombocytopenia 67% vs. 31%; grade 3/4 neutropenia 35% vs. 11%; grade 3/4 diarrhea 26% vs. 8%
Panobinostat + melphalan (Berenson et al.) ⁷⁷	1/2	40	15 – 20 mg PO TIW 1 week or 2 weeks, every 4 weeks	At least PR n=3; SD n=23, PD n=14	Grade 3/4 neutropenia 30.8%; grade 3/4 thrombocytopenia 23.1%
Panobinostat + melphalan + thalidomide + prednisone (Offidani et al.) ⁸⁰	1/2	31	10 – 20 mg PO TIW on a 3-weeks-on/1-week off schedule, every 4 weeks	CR n=2; VGPR n=2; SD n=11	Grade 3/4 neutropenia 71%; grade 3/4 thrombocytopenia 35%

Abbreviations: CBR, clinical benefit rate; CR, complete response; GI, gastrointestinal; nCR, near complete response; PD, progressive disease; VGPR, very good partial response

*CBR is defined as the percentage of patients with a confirmed response of MR or better.

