Worst Toxicity CTCAE Grade* unless otherwise specified (Value)		Dose Modification Guidelines At any time during a cycle of therapy (including intended day of dosing)
Neutropenia (ANC)	Grade 4 (ANC < 0.5 x 10 ⁹ /L)	Temporarily discontinue panobinostat dosing until resolved to ≤ grade 3, or baseline, then: 
 • If resolved within 7 days after suspending panobinostat, then restart panobinostat at an unchanged dose level • If resolved in more than 7 days after suspending panobinostat, then restart panobinostat reduced by one dose level
	Febrile neutropenia (ANC < 1.0 x 10 ⁹ /L, fever ≥ 38.5°C)	Temporarily discontinue panobinostat dosing until fever resolved and ANC ≤ grade 2, then restart panobinostat reduced by one dose level
NON-HEMATOLOGICAL TOXICITIES		
CARDIAC		
Cardiac - Prolonged QT interval**		Please refer to Section 7.4.3 .
GASTROINTESTINAL		
Diarrhea	Grade 2 (4-6 stools/day over baseline, etc) despite the use of optimal antidiarrheal medications	Temporarily discontinue panobinostat dosing until resolved to ≤ grade 1, or baseline, then restart at unchanged dose level
	Grade 3 (≥ 7 stools/day over baseline, etc) despite the use of optimal antidiarrheal medications	Temporarily discontinue panobinostat dosing until resolved to ≤ grade 1, or baseline, then restart panobinostat reduced by one dose level
	Grade 4 (life-threatening consequences, hemodynamic collapse, etc) despite the use of optimal antidiarrheal medications	Discontinue panobinostat dosing
Vomiting/Nausea***	Grade 1 & 2 not requiring treatment or controlled using standard anti-emetics	Maintain dose level
	Grade 3 or 4 vomiting or Grade 3 nausea that cannot be controlled despite the use of standard anti-emetics	Temporarily discontinue panobinostat dosing until resolved to ≤ grade 1, or baseline, then restart panobinostat reduced by one dose level

Fatigue		
Fatigue	Grade 3	Temporarily discontinue panobinostat dosing until resolved to \leq grade 2, or baseline, then: 
 • If resolved within 7 days after suspending panobinostat, then restart panobinostat at an unchanged dose level • If resolved in more than 7 days after suspending panobinostat, then restart panobinostat reduced by one dose level
	Grade 4	Temporarily discontinue panobinostat dosing until resolved to \leq grade 2, or baseline, then: 
 • restart panobinostat reduced by one dose level
HEPATIC		

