 # It is advised that the standard of care heptavalent pneumococcal conjugate vaccine be administered at around day +90 prior to the initiation of maintenance therapy.
 @ Archived (formalin-fixed paraffin embedded) bone marrow clot will be accessed to identify myeloma index clones for high-throughput sequencing.
 § Patients can be enrolled after autologous HCT without having the pre-HCT screening visit (which is not require).
 §§ Only grade ≥ 3 adverse event (AE) will be collected.
 §§§ Patients will be evaluated (history and physical) on day 5 of cycle 1.

Abbreviations: SOC, standard of care

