8.3.1 Adverse events

Information about unexpected grades ≥ 3 adverse events, whether volunteered by the subject, discovered by investigator questioning, or detected through physical examination, laboratory test or other means, will be collected and recorded and followed as appropriate.

An adverse event is the appearance or worsening of any undesirable sign, symptom, or medical condition occurring after starting the study drug even if the event is not considered to be related to study drug. Medical conditions/diseases present before starting study drug are only considered adverse events if they worsen after starting study drug. Abnormal laboratory values or test results constitute adverse events only if they induce clinical signs or symptoms, are considered clinically significant, or require therapy.

The occurrence of adverse events should be sought by non-directive questioning of the patient at each visit during the study. Adverse events also may be detected when they are volunteered by the patient during or between visits or through physical examination, laboratory test, or other assessments. As far as possible, each adverse event should be evaluated to determine:

1. the severity grade (moderate, severe) or (grade 3-4) – only grades adverse events will be reported its relationship to the study drug(s) (suspected/not suspected)
2. its duration (start and end dates or if continuing at final exam)
3. action taken (no action taken; study drug dosage adjusted/temporarily interrupted; study drug permanently discontinued due to this adverse event; concomitant medication taken; non-drug therapy given; hospitalization/prolonged hospitalization)
4. whether it constitutes a serious adverse event (SAE)

All adverse events should be treated appropriately. Such treatment may include changes in study drug treatment including possible interruption or discontinuation, starting or stopping concomitant treatments, changes in the frequency or nature of assessments, hospitalization, or

any other medically required intervention. Once an adverse event is detected, it should be followed until its resolution, and assessment should be made at each visit (or more frequently, if necessary) of any changes in severity, the suspected relationship to the study drug, the interventions required to treat it, and the outcome.

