12.1 Data collection and monitoring

Investigators must enter the information required by the protocol onto Case Report Forms (CRFs) for unexpected grades ≥ 3 adverse events and serious adverse events. Additional data to be captured may be identified at the time of study activation or review by ongoing monitoring committees.

13 Statistical methods

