13.1 Statistical methods and data analysis

This is an open label study of 2 different panobinostat maintenance dosing schedules after autologous HCT in patients with multiple myeloma. There are 2 cohorts and patients will be enrolled sequentially to cohort A, then to cohort B. The sample size is 30 patients for this trial (15 for each cohort). We expect that at least 2/3 of each cohort will complete 12 cycles of maintenance panobinostat (regardless of dose modification) and will be evaluable for the primary endpoint. The widths of 95% confidence interval (CI) are 0.356, 0.438, 0.487, 0.514, and 0.522 when the proportions of patients tolerating 12 cycles of maintenance are 0.9, 0.8, 0.7, 0.6, and 0.5, respectively.

A patient who withdraws from the study due to reasons other than death, disease progression or toxicity will be replaced and is considered as non-evaluable for primary endpoint. The proportion of patients tolerating the therapy will be reported with 95% CI. All 30 patients are eligible for secondary endpoints. We will compute the overall response rates before the transplant, after autologous HCT, and after the completion of maintenance therapy, and at best response. The OS and PFS will be estimated using the Kaplan-Meier method. We will also report the incidences of all grades and grade ≥ 3 toxicities. The two-sided 95% CIs for

proportion, and OS and PFS will be computed using the Clopper-Pearson method and the Greenwood formula, respectively. In addition, the frequency of B cell precursor as well as other cell subsets, and their 95% CI will be evaluated using t-distribution. If data do not meet normality assumption, the power transformation (e.g., log-transformation) will be conducted. Those patients who are not in CR before the transplant would be most suitable for T-effector activity analysis. This will be examined by the paired t-test or the Wilcoxon signed-rank test, depending on the data distribution.

Relative dose intensity (RDI) represents the ratio of the amount of a drug actually delivered [actual dose intensity (DI)] to the amount planned (planned DI). The purpose of calculating RDI is to evaluate whether the planned DI of a chemotherapy treatment was actually achieved which may suggest the feasibility of planned treatment regimen. There are multitude of reports demonstrating a correlation between RDI and survival in cancer treatment.

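### The toxicity incidence promised in 13.1 may under-count asymptomatic grade 3-4 cytopenias, because 8.3.1 filters laboratory values that section 7.4 grades by count

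*Combined protocol and SAP*

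**What the plan says.** The AE definition in 8.3.1 has a laboratory filter: "Abnormal laboratory values or test results constitute adverse events only if they induce clinical signs or symptoms, are considered clinically significant, or require therapy". The same section describes what is gathered: "Information about unexpected grades ≥ 3 adverse events, whether volunteered by the subject, discovered by investigator questioning, or detected through physical examination". Section 12.1 has investigators complete case report forms "for unexpected grades ≥ 3 adverse events and serious adverse events" and leaves further items to be identified at activation or by later committee review. In Table 8-1 the row for toxicity is labelled as AE assessment, and its footnote reads "Only grade ≥ 3 adverse event (AE) will be collected", without the restriction to unexpected events.

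Section 7.4 works from the count. Under Table 7-2 an ANC below 0.5 x 10⁹/L leads to "Temporarily discontinue panobinostat dosing until resolved to ≤ grade 3, or baseline", with no symptom required. Platelets below 25 x 10⁹/L also lead to a hold on the count alone; grade 3 platelets (25 to below 50) do so only with bleeding. Section 7.4.1 separately sets minimum ANC, hemoglobin and platelet values for starting each cycle.

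Section 13.1 then promises: "We will also report the incidences of all grades and grade ≥ 3 toxicities". It does not say whether these come from AE forms or from laboratory values.

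**The concern.** The safety profile is part of the primary objective (4.1, 13.1.3). Section 2.1.3 names thrombocytopenia, anemia and neutropenia, mostly grade 3/4, as the most frequent hematopoietic findings with this drug. Section 3 gives susceptibility to cytopenias after transplant as one reason for a low starting dose. These are the toxicities a reader will look for first.

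If the 13.1 incidence is tabulated from AE records, a grade 3-4 count without symptoms or treatment enters only when an investigator considers it significant. The plan gives no standard for that judgement, and the trial is open-label. The published hematologic incidence would then mix the frequency of low counts with the habit of recording them, and with 15 patients per cohort a few unrecorded cases change the figure materially.

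**Working it through.** **The plan's own figure.** Section 13.1 gives 95% CI widths of 0.356, 0.438, 0.487, 0.514 and 0.522 for proportions of 0.9, 0.8, 0.7, 0.6 and 0.5. Clopper-Pearson intervals with n = 15 and x = 15p reproduce all five. This confirms the interval method and n used below; it says nothing for or against the concern.

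**Two literal cases.**

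1. ANC 0.4, no fever, no growth factor, drug held 5 days. Table 7-2: grade 4, hold required. Section 8.3.1: an AE only if considered clinically significant. Section 13.1: counted only if it became an AE record, or if toxicity is read directly from counts, which no section says.
2. Platelets 30, no bleeding or transfusion. Table 7-2: grade 3, no mid-cycle action. Section 7.4.1: the platelet minimum of 50 would stop the next cycle from starting if the count persisted. Section 8.3.1: again an AE only by judgement.

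Both are grade 3 or 4 by count, and neither must appear in an AE-based incidence.

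**Illustrative size.** Base rates are from the single-agent phase 2 row of Table 2-4 (N = 38): "Grade 3/4 neutropenia 31.6%; grade 3/4 thrombocytopenia 26.3" percent. That study used weekly dosing in relapsed/refractory patients, so the rates are only indicative. The recorded share r is not in the documents; 10%, 25% and 50% are assumed.

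Expected true cases per cohort = 15 × p. Neutropenia: 15 × 0.316 = 4.7. Thrombocytopenia: 15 × 0.263 = 3.9.

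Expected reported cases = 15 × p × r. Chance that a cohort reports none = (1 − p × r)^15.

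| r | Neutropenia reported | Chance of none | Thrombocytopenia reported | Chance of none |
|---|---|---|---|---|
| 10% | 0.5 | 62% | 0.4 | 67% |
| 25% | 1.2 | 29% | 1.0 | 36% |
| 50% | 2.4 | 8% | 2.0 | 12% |

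Exact 95% intervals show what such a shift does to the report: 5/15 gives 12-62%, and 1/15 gives 0.2-32%.

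**A lower base rate.** Table 2-1 covers every-other-week dosing three times a week, which is Cohort A's schedule, at 30 mg and above. At 30 mg, neutropenia of any grade was 3 of 28 (10.7%), or 15 × 0.107 = 1.6 patients per cohort. Grade 3/4 could not exceed that, so reported cases at the same shares would be at most 0.2, 0.4 and 0.8. Any-grade thrombocytopenia was 10 of 28 (35.7%), or 5.4 of 15; the grade 3/4 part is not given. These are pooled AE reports from other studies, so they too are only indicative, but they show that 4.7 is not a neutral anchor for neutropenia.

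**The case against.** Section 13.1 speaks of toxicities, section 7.4 says toxicity is assessed by CTCAE, and Table 7-2 grades cytopenias by count. On that reading the 8.3.1 filter never reaches the incidence. Section 8.3 also lists hematology and chemistry monitoring separately from AE recording. This reading is possible, but Table 8-1 equates toxicity with AE assessment and 12.1 does not name laboratory values for capture, so the ambiguity stands.

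A count that forces a hold may well be judged significant. Section 8.3.1 lists interruption of study drug among the actions taken for an AE and expects some AEs to be found by laboratory test. That weakens the first case above, but no sentence makes a hold sufficient.

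Holds, delays and reductions are reported per cohort and enter the relative dose intensity (13.1), so cytopenias that disrupt dosing stay visible there. This stands for dose delivery. It need not show grade or incidence, and it misses grade 3 counts that recover without delaying a cycle.

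The restriction to unexpected events in 8.3, 8.3.1 and 12.1 already removes many of the same cytopenias, which are expected with this drug. The overlap is real. The laboratory filter would nevertheless remain if that word were deleted, and it applies under the Table 8-1 footnote, which omits the word.

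Three stronger inferences are not supported. A reader might infer that asymptomatic cytopenias will be lost; the text shows only that they may be. A reader might infer that the Table 2-4 rates are count-based and so cannot be compared with this trial's; no section says how they were derived, and 2.2.2 describes some of that table's trials in AE terms. A reader might infer a bias between cohorts; nothing in the documents shows that judgement would differ between A and B, and no between-cohort test is planned.

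**Conclusion.** The concern holds as a possible under-count of asymptomatic grade 3-4 cytopenias in the 13.1 toxicity incidence. It rests on three features of the text: an AE filter with an undefined judgement criterion, toxicity treated as AE data in Table 8-1 and 12.1, and no rule deriving toxicity from counts. Its size cannot be fixed from the documents. The illustrated drop, from 4.7 to between 0.5 and 2.4 neutropenia cases per cohort and from 3.9 to between 0.4 and 2.0 thrombocytopenia cases, depends on assumed recorded shares of 10-50% and on borrowed weekly-schedule rates, which Table 2-1 suggests are too high for neutropenia.

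The proportion completing 12 cycles and the relative dose intensity do not depend on AE status. The 40% suspension trigger in 13.1.5 is non-hematologic, so cytopenias do not enter it. What is at risk is the hematologic part of the safety profile. It should be corrected because the remedy is cheap.

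**What to change.** In 13.1, state that hematologic and chemistry toxicity will be derived by applying CTCAE 4.03 limits to every recorded CBC and CMP value, summarised as worst grade per patient, by cohort, in all dosed patients, whether or not an AE was recorded. In 12.1, add these values to the data captured. Keep the 8.3.1 rule for AE reporting only. No treatment rule changes.

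This also supplies the all-grades incidence for laboratory toxicities, which AE records limited to grade ≥3 cannot. It does not do so for non-laboratory toxicities, and it does not settle the unexpected-events restriction, which needs its own correction. The derived figure covers only counts actually drawn; Table 8-1 schedules weekly CBCs in cycles 1 and 2 only.

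The cost is entry or electronic transfer of results from samples already scheduled, and a hematologic toxicity figure that will probably look less favourable.

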8.3.2 Vital signs

Vital sign assessment consists of height (first visit), pulse, blood pressure, respiration rate, temperature and weight. Blood pressure, pulse and respiration rate should be measured on patients after at least 3 minutes in the sitting position

8.3.3 Physical examination

Physical examination will be performed which comprises examination of skin, lungs, heart, abdomen, lymph nodes, and extremities at minimum.

Significant findings made after the start of study drug which meet the definition of an grades ≥ 3 Adverse Event must be recorded.

8.3.4 Laboratory evaluations

Laboratory evaluation should be done at baseline (within ≤ 72 hours prior to dosing prior to the first administration of oral LBH589), during the course of the study and at the time of the study treatment completion visit. Results must be reviewed prior to administering LBH589. More frequent examinations may be performed if medically indicated; results should be recorded.

Hematology

Hematology must include hemoglobin, hematocrit, platelets, total white blood cell count (WBC) and differential. The coagulation profile includes a prothrombin time or International Normalized Ratio (INR), activated partial thromboplastin time and fibrinogen.

Blood chemistry

Biochemistry includes the following parameters: BUN, creatinine, sodium, potassium, chloride, CO₂ (HCO₃), glucose, calcium, albumin, total protein, total bilirubin, alkaline phosphatase, LDH, AST/SGOT, ALT/SGPT, phosphorous, magnesium. If total bilirubin is greater than the upper limit of normal, direct and indirect bilirubin may be performed. Biochemistry tests should be obtained after patient has fasted, if possible.

Urinalysis

Standard urinalysis dipstick assessment (pH, protein, glucose, blood, ketones, and leukocytes) should be performed. This must be supplemented with laboratory quantification of any potentially relevant abnormalities.

Thyroid function test

Thyroid Stimulating Hormone (TSH) and free T4 (thyroxine) will be measured at baseline and at study treatment completion.

8.3.5 Serum pregnancy test

All females of childbearing potential should complete a serum pregnancy test within 7 days prior to the administration of LBH589 on day 1 of cycle 1. The pregnancy test should be repeated in week 1 of every cycle (except for cycle 1). Postmenopausal women must have been amenorrheic for ≥ 12 months in order to be considered “of non-childbearing potential”.

8.3.6 ECG

A screening 12-lead ECG will be performed to assess study eligibility. Additional 12-lead ECGs will be performed at a minimum at scheduled time points as indicated in Table 8-2. Pre-dose ECG monitoring is required for the first four cycles of treatment. Post-dose ECGs will be required during cycle one, on days 1 and 5. Additional ECG monitoring should be done at the discretion of the Investigator, as clinically indicated. All ECGs will be read locally.

Table 8-2 Cardiac assessment monitoring schedule

Cycle	Day of cycle	ECG monitoring ^a
	Screening ^b	Single ECG to assess eligibility
Cycle 1	1, 5	Pre-dose: Single 12 lead ECG
	1, 5	3 hours (± 15 minutes) post dose: Single 12 lead ECG
Cycle 2 and beyond	1	Pre-dose: Single 12 lead ECG
^a Refer to Table 7-3 for the recommended dose modifications due to QTc interval prolongation ^b The screening ECGs will be analyzed locally to assess eligibility of the patient. (Note: the mean QTc interval at baseline must be ≤ 470 msec for the patient to be eligible for participation in the trial) Note: If no significant QTcF prolongation is noted during the first 4 cycles, the QTc monitoring is no longer required and may be performed at the Investigator’s discretion, if medically indicated.		

All cardiac events should be treated as per the local standard of care and referred to a specialist if clinically indicated. The localized readings of ECGs will use the Fridericia correction with MUSE system: QTcF. Any final decisions concerning dose modifications or permanently discontinuing the patient from study drug due to QTcF prolongation will be based on the assessment performed by the Investigators using QTcF correction derived from MUSE system. Any plan to deviate from these guidelines should be previously discussed and

agreed upon with Novartis. If a patient cannot be dosed due to prolonged QTcF for more than 7 days since last dose, patient should be discontinued from study.

8.3.6.1 Performance status

Performance status will be assessed using Karnofsky performance score at baseline, at day 1 of each cycle and at the end of stud visit.

8.4 Drug levels and pharmacokinetic assessments

- Drug levels and pharmacokinetic assessments will not be performed as part of this study.

9 Correlative studies

9.1 Assessment of minimal residual disease and B cell precursors

Aliquots of 50uL bone marrow aspirate in sodium heparin will be incubated in the dark for 15 minutes at room temperature with combination of fluorescent-labeled antiobodies, followed by red blood cell lysis with FACS lysing solution (BD biosciences). Cytoplasmic staining will be performed by permeabilizing cells with Fix & Perm reactives (Caltag), followed by incubation in the dark with fluorescent-labeled antibodies for 5 minutes at 4°C. Standarized 10-color antibody combinations will be used (Pac Blue/Krome Orange/FITC/PE/ECD/PerCP-Cy5.5/CD7-PE-Cy7/APC/APC-Alexa-Fluor-700/APC-Alexa-Fluor 750), including an isotype control tube plus 4 tubes:

- cytoplasmic-κ/cytoplasmic-λ/CD56/CD138/isotype/CD20/CD19/CD117/CD38/CD45
- CD49d/CD52/CD13/Cd138/CD33/CD40/isotype/CD44/CD38/CD45
- CD28/CD81/CD27/CD138/isotype/CD200/isotype/CD117/CD38/CD45
- isotype/CD319/CD56/CD138/isotype/CD269/CD19/CD117/CD38/CD45

Stained cells will be resuspended in phosphate buffered saline containing 2% paraformaldehyde. At least 500,000 events were acquired on a Gallios 10-color flow cytometer (Beckman Coulter). Flow cytometry data will be analyzed on ad-hoc templates created on Kaluza version 1.2 (Beckman Coulter) using standardized gating strategies to identify and characterize neoplastic clonal plasma cells, residual benign plasma cell populations, maturing B-cell precursors and mature B-cells. In particular, B-cells will be analyzed to identify putative clonal stem cell populations.

Peripheral blood and peripheral blood stem cell graft samples will also be collected, and multi-parameter flow cytometry will be performed for phenotype characterization of B cell precursors as described above.

Pharmacodynamic effects on various cell subtypes and evaluation of protein acetylation with panobinostat maintenance therapy

In order to determine whether 2 different panobinostat maintenance dosing schedules have any correlation with HDACs enzymatic activity, we will evaluate HDAC enzymatic activity in peripheral blood from patients. Peripheral blood samples will be obtained at baseline (before starting panobinostat), on day 5 of cycle 1, at cycle #6 and after the completion of maintenance. To this end we will use a HDAC fluorimetric cellular activity assay (Biomol, Catalog # AK503). A fluorogenic-cell permeable substrate, Fluor de Lys, is added to peripheral blood mononuclear cells (PBMC) grown in patient's serum and enter the cells where if there is remaining HDAC activity, the fluor de lys gets deacetylated producing a fluorescent signal. A detergent is used to allow contact between the non-cell permeable developer and both intra and extracellular deacetylated substrate. In addition, the HDACi trichostatin A is added along with the detergent to insure that no deacetylation occurs after cell lysis. To run this test approximately 1×10^5 PBMC are required/sample.

In order to determine the level of protein acetylation and more specifically of hyper-acetylated histones (H3 and/or H4), we will use a multiparameter flow cytometry assay for peripheral blood mononuclear cells. If acetyl-group removal from HDAC substrates is blocked we speculate that will lead to an overall increase in the number of acetylated proteins being the vast majority of these proteins the histones in cells population in peripheral blood. The blood leukocyte count will be obtained using a Coulter A^c-T Hematology analyzer. Multiparameter staining protocol will be adjusted from Chun and/or Ronzoni et al. In summary, whole blood will be collected at baseline, on day 5 of cycle 1, at cycle #6 and after the completion of panobinostat maintenance therapy. PBMCs ($5-10 \times 10^6$) will be obtained by gradient separation on Ficoll-Paque. Aliquots of PBMs will be briefly incubated with Zombie Yellow (Biolegend) to stain and gate-out non-viable cells. Cells will then be washed and incubated with antibodies conjugated to methanol-resistant fluorophore (BD Horizon V450/Brilliant Violet-711-FITC/Alexa Fluor 647) on a 2-tube/4-color panel for surface antigens: CD3/CD4/CD8/CD19 and CD3/CD7/CD45/CD14. Stained cells will be fixed in 2% formaldehyde for 30 min at 4°C and then permeabilized in 100% ice-cold methanol for 10 minutes at 4°C. After fixation and permeabilization, cells will be stained with anti-acetyl histone H3 and anti-acetyl tubulin, conjugated to PE and PerCP-Cy5.5, respectively. Events will be acquired on a FACSDiva flow-cytometer (BD) and analyzed on Kaluza v1.2 (Beckman Coulter) with appropriate controls. Gating strategies will be devised using surface markers to assess the level of acetyl histone H3 and acetyl tubulin on CD4 T-cells, CD8 T-cells, NK cells, B-cells, monocytes and neutrophils.

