4.2 Secondary

- To evaluate the complete response rate to panobinostat maintenance therapy after autologous HCT.
- To determine the 2-year PFS and OS of autologous HCT followed by panobinostat maintenance therapy in patients with multiple myeloma.
- **Exploratory secondary objectives:**
 - To evaluate histone acetylation (H3 and/or H4) of peripheral blood mononuclear cells
 - To isolate and identify clonotypic B cell progenitors in multiple myeloma patients from the bone marrow, peripheral blood and stem cell grafts.
 - To evaluate T-cell immune response against known myeloma tumor associated antigens while on panobinostat maintenance.
 - To evaluate humoral immunity against pneumococcal serotypes included in the standard of care heptavalent pneumococcal conjugate vaccine, and to assess cellular immune responses against CRM adjuvant found in the heptavalent pneumococcal conjugate vaccine.
 - To evaluate minimal residual disease (MRD) after autologous HCT followed by panobinostat maintenance therapy using flow cytometry
 - To evaluate MRD after autologous HCT followed by panobinostat maintenance therapy using multiplex PCR for CDR3 sequences

5 Overall study design

This is an open-label trial to determine the safety and tolerability of 2 different dosing schedules of single agent panobinostat maintenance therapy in patients with multiple myeloma who underwent high-dose melphalan followed by autologous HCT in patients with multiple myeloma. It is unknown whether the toxicity profile of panobinostat will be accentuated in patients after autologous HCT in the setting of maintenance therapy, hence the dose chosen for maintenance therapy is lower than MTD dosing or other phase 2 studies. There are 2 dosing schedules evaluated in this protocol in order to assess optimal tolerable schedule for panobinostat maintenance therapy after autologous HCT. As secondary

objectives, we will evaluate response after completion of treatment, and 2-year PFS and OS. As correlative studies, we plan to evaluate MRD, and to assess clonotypic B cells following an autologous HCT. We also plan to evaluate T effector immune response after autologous HCT while on panobinostat maintenance therapy.

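### Section 9.1 lists neutrophils for the acetylation readout but stains only Ficoll-separated mononuclear cells, so any neutrophil result would rest on a small, unrepresentative residual fraction

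*Combined protocol and SAP*

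**What the plan says.** The exploratory objective in Section 4.2 is "To evaluate histone acetylation (H3 and/or H4) of peripheral blood mononuclear cells". Section 9.1, in the part on pharmacodynamic effects and protein acetylation, describes one workflow for it:

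- **Assay material:** "we will use a multiparameter flow cytometry assay for peripheral blood mononuclear cells".
- **Sampling:** "whole blood will be collected at baseline, on day 5 of cycle 1, at cycle #6", and again once maintenance is complete.
- **Preparation:** the mononuclear cells, 5 to 10 million of them, "will be obtained by gradient separation on Ficoll-Paque".
- **What is stained:** "Aliquots of PBMs will be briefly incubated with Zombie Yellow (Biolegend) to stain and gate-out non-viable cells". The same cells are then surface-stained, fixed, permeabilized and stained for acetyl histone H3 and acetyl tubulin.
- **Surface panel:** two tubes, "CD3/CD4/CD8/CD19 and CD3/CD7/CD45/CD14".
- **Readout:** both acetylation markers are to be measured, by gates still to be devised, in six populations. The first two are the T-cell subsets defined by CD4 and by CD8; the list then closes with "NK cells, B-cells, monocytes and neutrophils".

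**The concern.** The preparation and the readout do not fit together. Separating mononuclear cells on a density gradient is meant to leave granulocytes behind, yet a granulocyte population is then listed for measurement in the retained fraction. Events falling in a neutrophil gate would be whatever granulocytes happened to stay in the mononuclear layer.

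That residue can differ between samples. A change from baseline to cycle 1 day 5, cycle 6 or the end of maintenance could then reflect which cells survived the separation as much as any effect of panobinostat. What is at stake is one exploratory result that would carry the label of a circulating cell type without representing it.

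**Working it through.** The plan gives no figure to reproduce, and no sample size, error rate or power enters. The check is to follow the sample through Section 9.1 and compare each listed population with the material that is stained and with the panel.

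**1. Is each population mononuclear, and does the panel mark it?**

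| Population | Mononuclear? | Panel markers available |
|---|---|---|
| CD4 T-cells | yes | CD3, CD4 |
| CD8 T-cells | yes | CD3, CD8 |
| NK cells | yes | CD7 without CD3 |
| B-cells | yes | CD19 |
| Monocytes | yes | CD14 |
| Neutrophils | no | no granulocyte-specific marker; only CD45/CD14 with light scatter |

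Five of the six populations belong to the prepared fraction and one does not. The marker column is my reading of the panel, since the protocol does not yet define the gates.

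**2. Is there another preparation that could supply neutrophils?** None is described for this assay. Whole blood is collected, but the stained aliquots are the separated cells. The red-cell lysis in Section 9.1 belongs to the minimal residual disease and B-cell precursor panels. The HDAC activity assay in Section 9.1 and the T-cell phenotyping in Section 9.2 also use mononuclear cells, and neither claims a neutrophil result.

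**3. Does the objective need neutrophils?** No. Section 4.2 is confined to mononuclear cells, so the neutrophil readout goes beyond the objective as well as failing to match the preparation.

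**4. Extent.** Six populations at four time points give 6 × 4 = 24 population-by-time readouts per patient for each acetylation marker. Neutrophils account for 1 × 4 = 4 of these, or one sixth. The other 20 are unaffected.

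**The case against.** The strongest reply has four parts.

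- **Residual cells exist.** A reader might infer that a neutrophil readout is impossible. That is too strong: some low-density granulocytes can remain in the mononuclear layer and could be gated. What stands is that they are a small and unrepresentative subset.
- **The description is abbreviated.** Section 9.1 presents it as a summary, says the staining will be adapted from two published methods, and leaves the gating to be devised. Those methods might retain granulocytes, but I could not find them in the Section 16 reference list, and the text as written directs staining of separated cells only. Depletion of neutrophils by the gradient is general laboratory knowledge, not a statement in the protocol.
- **The schedule comparison does not depend on it.** A reader might infer that a comparison of the two dosing schedules is compromised. Section 9.1 states the two-schedule purpose for HDAC enzymatic activity, a separate assay. For acetylation the stated purpose is to determine its level, and Sections 13.1 and 13.1.4 specify neither a between-cohort test of acetylation nor a neutrophil-specific analysis.
- **Safety does not depend on it.** Because neutropenia is a frequent finding with this drug, a reader might infer a consequence for toxicity assessment. Nothing in the documents links neutrophil acetylation to neutropenia or to dosing. Neutrophil counts are followed through the hematology tests in Section 8.3.4 and acted on under Table 7-2, independently of this assay.

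These points limit the consequence. They do not remove the mismatch between the cells prepared and the cells listed.

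**Conclusion.** The inconsistency is real and small. Followed as written, Section 9.1 gives a neutrophil acetylation value that does not represent circulating neutrophils: one of six populations, at all four time points, in both cohorts. The five mononuclear populations, the Section 4.2 objective, the primary endpoint, the sample size and safety monitoring are unaffected.

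The conclusion rests on two assumptions: that the Ficoll-Paque step performs as such gradients ordinarily do, and that no granulocyte-retaining preparation is planned beyond what the protocol describes. The size of the residual fraction is not given in the documents and is not needed for the conclusion. This is a minor correction, best made before samples are processed, because a representative neutrophil readout cannot be recovered later from stored mononuclear cells.

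**What to change.** **Preferred:** delete neutrophils from the population list in Section 9.1, so that it matches the mononuclear-cell objective in Section 4.2. The cost is one exploratory readout, with no laboratory work. Because the method sits in the protocol body, Section 11 requires a written amendment reviewed by the supporting company and the investigator; editing laboratory instructions alone would not be enough. Section 15.1 adds ethics committee approval unless the amendment counts as administrative.

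**Only if a neutrophil readout is wanted:** specify a red-cell-lysed aliquot of the blood already drawn, taken before the gradient, with a stated neutrophil gate or an added marker. Two things need confirming first:

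- **Volume.** Table 9-1 provides only 2 green-top tubes on cycle 1 day 5, against 1 tiger-top and 6 green-top tubes at the other blood draws. The day 5 tubes already have to supply about 100,000 mononuclear cells per sample for the HDAC activity assay and 5 to 10 million for acetylation. Tube volumes and cell yields are not stated, so whether blood is left over is unknown.
- **Staining.** The fixation and methanol permeabilization would need a short check on lysed whole blood.
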